5.6.5. Blinding

It is not feasible to blind treatment allocations for individual subjects because of different routes of administration, different treatment schedules and different adverse event profiles between quizartinib and salvage chemotherapy. The primary endpoint of overall survival is a robust endpoint and bias due to lack of blinding should be minimal. To further reduce any potential bias, the Sponsor will not have access to aggregate efficacy data except when data from both treatment (quizartinib) and control (salvage chemotherapy) arms are combined. Data relating to the primary endpoint of survival will be restricted so that the Sponsor will not have access to long-term follow-up data on individual subjects, which begins 30 days after discontinuing study treatment in either treatment arm. Approximately 80% of the planned events are expected to occur during this long-term follow-up period and therefore the Sponsor will be blinded to full data supporting the primary endpoint of the study.

5.6.6. Prior and Concomitant Therapy

All concomitant medications administered from the Screening visit through the 30-Day Follow-up visit or until the start of additional AML therapy will be recorded on the appropriate CRF. Refer to Section 5.6.6.1 for prohibited medications and Section 5.6.6.2 for allowed supportive therapy.

5.6.6.1. Prohibited Medications

For all subjects (quizartinib and salvage chemotherapy): Administration of other antineoplastic agents during the study period is prohibited with the exception of hydroxyurea which is allowed for up to 14 days prior to or for up to 4 days concomitantly with quizartinib or salvage chemotherapy to control the peripheral blast count, up to a maximum dose of 5 g/day.

In subjects receiving quizartinib:

- Concomitant medications that prolong the QT/QTc interval are prohibited except when regarded by the Investigator as essential for subject care.
- Strong CYP3A4 inhibitors should be avoided but are not prohibited although require a quizartinib dose adjustments are required. Weak or moderate CYP3A4 inhibitors, such as fluconazole, may be used without dose reduction.
- Concomitant strong or moderate CYP3A4 inducers are prohibited.

If quizartinib is co-administered with drugs that inhibit P-gp, increased concentrations of quizartinib are possible and caution should be exercised. The co-administration of P-gp inhibitors and inducers with quizartinib should be avoided if possible. If quizartinib is co-administered with drugs that are substrates of P-gp, increased concentrations of the substrate drugs are possible and caution should be exercised.

Prohibited medications and foods are listed in [Appendix 1: List of Potential QT Prolonging Drugs, CYP3A4 Inhibitors/Inducers, and P-glycoprotein Inhibitors/Inducers](#).

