If any of the following criteria are met, the quizartinib dose will be reduced stepwise from 60 mg/day to 30 mg/day or from 30 mg/day to 20 mg/day or discontinued. No further dose reductions below 20 mg/day will be allowed.

- **QTcF prolongation**

- Grade 2 (QTcF average of triplicate readings > 480 msec) (All toxicity grades according to National Cancer Institute Common Terminology Criteria for Adverse Events [NCI CTCAE] v4.03)
 - The dose will be reduced without interruption.
 - If 20 mg/day is the current dose, dosing will be interrupted for up to 14 days. If QTcF returns to within 30 msec of baseline or ≤ 450 msec within 14 days, treatment may be resumed at 20 mg/day.
- Grade 3 (QTcF average of triplicate readings > 500 msec)
 - Dosing will be interrupted for up to 14 days. If QTcF returns to within 30 msec of baseline or ≤ 450 msec within 14 days, treatment may be resumed at a reduced dose.
 - If 20 mg/day is the current dose, dosing will be interrupted for up to 14 days. If QTcF returns to within 30 msec of baseline or ≤ 450 msec within 14 days, treatment may be resumed at 20 mg/day. If Grade 3 event returns, treatment will be discontinued.
- Grade 4 (QTcF > 500 msec or > 60 msec change from baseline, and Torsade de pointes or polymorphic ventricular tachycardia or signs/symptoms of serious arrhythmia)
 - Treatment will be discontinued.

- **Non-hematologic toxicity**

- Grade 3 or 4 related to quizartinib and persisting >48 hours without improvement to \leq Grade 2
 - Dosing will be interrupted for up to 14 days.
 - If toxicity improves to \leq Grade 1 within 14 days, treatment may be resumed at the reduced dose.

- **Myelosuppression**

- In a subject with CRp or CRi, the dose may be reduced at the Investigator's discretion if:
 - The subject has been treated for a minimum of 2 cycles.
 - Platelet count is $<100 \times 10^9/L$ and absolute neutrophil count (ANC) is $\leq 1000 \times 10^9/L$.

- Marrow blasts < 5%.
- There is no evidence of extramedullary disease.
- **Initiation of concomitant treatment with a strong CYP3A4 inhibitor**
 - The dose will be reduced from either 60 mg/day to 30 mg/day or from 30 mg/day to 20 mg/day.
 - A subject taking a strong CYP3A4 inhibitor at time of randomization will initiate quizartinib administration at 20 mg/day.

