5.2.4. Quizartinib Dose Reduction with Strong CYP3A4 Inhibitors

Data from Study AC220-015, which examined the effect of strong and moderate CYP3A4 inhibitors on quizartinib PK in human volunteers, show that concomitant ketoconazole, a strong

CYP3A4 inhibitor, increased quizartinib AUC_{0-inf} and steady state C_{max} (after repeat daily dosing) approximately 2-fold, and concomitant fluconazole, a moderate CYP3A4 inhibitor, increased quizartinib AUC_{0-inf} and steady state C_{max} approximately 1.2-fold. Subjects receiving concomitant medication with a strong CYP3A4 inhibitor on Day 1, and who are randomized to quizartinib, will take 20 mg/day. Subjects who begin treatment with a strong CYP3A4 inhibitor while receiving quizartinib will be required to be reduced from either 60 mg/day to 30 mg/day or from 30 mg/day to 20 mg/day. If the subject discontinues the strong CYP3A4 inhibitor, the dose of quizartinib can be resumed at the prior dose. No dose reduction of quizartinib is required when subjects are co-administered a moderate or weak CYP3A4 inhibitor. See [Appendix 1: List of Potential QT Prolonging Drugs, CYP3A4 Inhibitors/Inducers, and P-glycoprotein Inhibitors/Inducers](#).

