5.6.4.4. Quizartinib Dose Reduction Rules and Definitions

The dose of quizartinib will be reduced stepwise from 60 mg/day to 30 mg/day or from 30 mg/day to 20 mg/day, based on the following criteria:

QTcF (QT interval corrected with Fridericia's formula) Prolongation

- Grade 2 (QTcF average of triplicate readings > 480 msec)
 - The dose will be reduced without interruption.
 - If 20 mg/day is the current dose, dosing will be interrupted for up to 14 days. If QTcF returns to within 30 msec of baseline or ≤ 450 msec within 14 days, treatment may be resumed at 20 mg/day.
- Grade 3 (QTcF average of triplicate readings > 500 msec)
 - Dosing will be interrupted for up to 14 days. If QTcF returns to within 30 msec of baseline or ≤ 450 msec within 14 days, treatment may be resumed at a reduced dose.
 - If 20 mg/day is the current dose, dosing will be interrupted for up to 14 days. If QTcF returns to within 30 msec of baseline or ≤ 450 msec within 14 days, treatment may be resumed at 20 mg/day. If Grade 3 event returns, treatment will be discontinued.
- Grade 4 (QTcF >500 msec or >60 msec change from baseline, and Torsade de pointes or polymorphic ventricular tachycardia or signs/symptoms of serious arrhythmia)
 - Treatment will be discontinued.

See Section 8.5 for clinical guidelines for the management of QT prolongation.

Non-hematologic Toxicity

Grade 3 or 4 related to quizartinib and persisting >48 hours without improvement to \leq Grade 2.

- Dosing will be interrupted for up to 14 days.

- If toxicity improves to \leq Grade 1 within 14 days, treatment may be resumed at the reduced dose.

Myelosuppression

In a subject with CRp or CRi, the dose may be reduced at the Investigator's discretion if:

- The subject has been treated for a minimum of 2 cycles.
- Platelet count is $<100 \times 10^9/L$ and ANC is $\leq 1000 \times 10^9/L$.
- Marrow blast count is $<5\%$.
- There is no evidence of extramedullary disease.

Initiation of concomitant treatment with a strong CYP3A4 inhibitor is identified in [Appendix 1: List of Potential QT Prolonging Drugs, CYP3A4 Inhibitors/Inducers, and P-glycoprotein Inhibitors/Inducers](#).

The dose will be reduced one level (60 mg to 30 mg or 30 mg to 20 mg) when treatment with a strong CYP3A4 inhibitor is initiated.

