Antipsychotics	thioridazine mesoridazine chlorpromazine prochlorperazine trifluoperazine fluphenazine perphenazine pimozide risperidone ziprasidone lithium haloperidol
Tricyclic/tetracyclic antidepressants	amitriptyline desipramine doxepin dosulepin hydrochloride imipramine maprotiline
Selective serotonin and norepinephrine reuptake inhibitors (SSNRIs)	venlafaxine
Macrolide antibiotics	azithromycin erythromycin

	clarithromycin dirithromycin roxithromycin tulathromycin
Fluoroquinolone antibacterials	moxifloxacin gatifloxacin
Azole antifungals	ketoconazole fluconazole itraconazole posaconazole voriconazole
Antimalarials	amodiaquine atovaquone chloroquine doxycycline halofantrine mefloquine proguanil primaquine pyrimethamine quinine sulphadoxine
Antiprotozoals	pentamidine
Antiemetics	droperidol dolasetron granisetron ondansetron
Antiestrogens	tamoxifen
Immunosuppresants	tacrolimus

CYP3A4 Inhibitors

Inhibitor Type	Generic Drug Name	Comments
Strong	boceprevir clarithromycin conivaptan grapefruit grapefruit juice indinavir itraconazole ketoconazole lopinavir mibefradil nefazodone nelfinavir posaconazole ritonavir saquinavir telaprevir telithromycin voriconazole	Use prohibited for subjects receiving quizartinib unless necessary for patient care in which case a dose reduction of quizartinib is required
Moderate	amprenavir aprepitant atazanavir ciprofloxacin crizotinib darunavir diltiazem erythromycin fluconazole fosamprenavir imatinib verapamil	Use allowed. No requirement for quizartinib dose reduction
Weak	alprazolam amiodarone amlodipine atorvastatin bicalutamide cilostazol cimetidine cyclosporine fluoxetine fluvoxamine ginkgo goldenseal isoniazid lapatinib oral contraceptives	Use allowed. No requirement for quizartinib dose reduction

	nilotinib pazopanib ranitidine ranolazine ticagrelor tipranavir zileuton	
--	--------------------------------------------------------------------------------------------	--

CYP3A4 Inducers

Inducer Type	Generic Drug Name	Comments
Strong	avasimibe carbamazepine phenytoin rifampin St. John's wort	Use prohibited for subjects receiving quizartinib
Moderate	bosentan efavirenz etravirine modafinil nafcillin	Use prohibited for subjects receiving quizartinib
Weak	amprenavir aprepitant armodafinil clobazam echinacea pioglitazone prednisone rufinamide vemurafenib	Use allowed.

P-glycoprotein Inhibitors/Inducers

Inhibitors	Inducers

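### The concomitant-medication rules conflict for a subject already at 20 mg/day who starts a strong CYP3A4 inhibitor, and for drugs that are both restricted and marked as allowed

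*Combined protocol and SAP*

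**What the plan says.** **Strong CYP3A4 inhibitors and dose.** Section 5.6.4.4 sets the rule for starting one: "The dose will be reduced one level (60 mg to 30 mg or 30 mg to 20 mg) when treatment with a strong CYP3A4 inhibitor" (quoted in part). Section 5.2.4 gives the same two steps. The synopsis adds a floor: "No further dose reductions below 20 mg/day will be allowed". The strong-inhibitor row of Appendix 1 reads: "Use prohibited for subjects receiving quizartinib unless necessary for patient care in which case a dose reduction of quizartinib is required". Section 5.6.6.1 is milder: strong inhibitors are to be avoided but are not prohibited, and a dose adjustment is needed. Section 5.2.4 reports that ketoconazole roughly doubled quizartinib AUC and steady-state Cmax in volunteers, and that fluconazole raised them about 1.2-fold.

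**QT-prolonging drugs.** Section 5.6.6.1 states: "Concomitant medications that prolong the QT/QTc interval are prohibited except when regarded by the Investigator as essential for subject care". It refers to Appendix 1 for the list. The azole row of the QT list there is "ketoconazole fluconazole itraconazole posaconazole voriconazole"; erythromycin appears under macrolides and amiodarone under Class III antiarrhythmics. The next bullet of Section 5.6.6.1 says: "Weak or moderate CYP3A4 inhibitors, such as fluconazole, may be used without dose reduction". In the Appendix 1 CYP3A4 table, fluconazole and erythromycin (moderate) and amiodarone (weak) carry the comment "Use allowed. No requirement for quizartinib dose reduction".

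**Antineoplastics.** Section 5.6.6.1 bars other antineoplastic agents for all subjects, with hydroxyurea as the only exception. Appendix 1 marks imatinib and crizotinib (moderate inhibitors), nilotinib, pazopanib, lapatinib and bicalutamide (weak inhibitors) and vemurafenib (weak inducer) as allowed.

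**The concern.** A site needs one answer to two questions: may this drug be given, and what happens to the quizartinib dose if it is? For the drugs above, the answer depends on which page is read.

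The 20 mg/day case matters most. A subject can be at that dose because quizartinib was already reduced, for instance from 30 mg for Grade 2 QTcF prolongation. If a strong inhibitor is then needed, one text requires a reduction and another forbids it. Five of the listed strong inhibitors (ketoconazole, itraconazole, posaconazole, voriconazole, clarithromycin) are themselves on the QT list.

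The protocol's own data show why clarity is needed. Section 3.3 reports one Torsades case in the earlier Phase 2 study, at 90 mg with a concurrent strong CYP3A4 inhibitor. Table 2 shows QTcF increases above 60 msec in 3% of subjects at 30 mg and 19% at 60 mg.

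**Working it through.** **Step 1. The 20 mg/day texts side by side.**
- Appendix 1: if a strong inhibitor is necessary, a quizartinib reduction is required, at any current dose.
- Sections 5.6.4.4 and 5.2.4: steps from 60 to 30 mg and from 30 to 20 mg, with none from 20 mg.
- Synopsis: no reduction below 20 mg/day.

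At 60 or 30 mg the texts are compatible. At 20 mg the first and third cannot both be followed, and the second is silent.

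**Step 2. Size.** The 2-fold figure comes from a pharmacokinetic study whose data are not in the documents, so it cannot be reproduced and is taken as given. Section 3.3 states dose proportionality for 30 to 90 mg; extending it to 20 mg is an assumption. The 1.8 to 2.2 range is also an assumption.

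Exposure ratio = (dose with inhibitor × fold increase) / dose before inhibitor.
- 60 to 30 mg: 30 × 2 / 60 = 1.00 (0.90 to 1.10)
- 30 to 20 mg: 20 × 2 / 30 = 1.33 (1.20 to 1.47)
- 20 mg unchanged: 20 × 2 / 20 = 2.00 (1.80 to 2.20)

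In the last case the subject has the parent-drug exposure of about 40 mg (36 to 44 mg). For someone reduced from 30 mg because of QTcF, that is 40 / 30 = 1.33 times the exposure at the dose that led to the reduction (1.20 to 1.47).

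**Step 3. What else acts at 20 mg/day.** Section 5.6.4.4 interrupts dosing at Grade 2 or 3 QTcF prolongation and discontinues if Grade 3 returns or at Grade 4. Section 8.5 requires review of QT-prolonging drugs from Grade 2. All of these are triggered by observed prolongation. Weekly triplicate ECGs for 2 weeks are required after a dose escalation (Section 5.6.4.3), but no such rule is tied to starting an inhibitor. From Cycle 4, scheduled ECGs fall on Day 1 of each cycle (Table 3), and extra ones are at the investigator's discretion (Section 8.4).

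**Step 4. Cross-match of the Appendix 1 lists.**
- On the QT list and also marked allowed as moderate or weak CYP3A4 inhibitors: fluconazole, erythromycin, amiodarone (3).
- Antineoplastics marked allowed: imatinib, crizotinib, nilotinib, pazopanib, lapatinib, bicalutamide, vemurafenib (7).
- Text stating that one list overrides another, or that the restrictions are cumulative: none found.

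The bicalutamide conflict could arise in practice. Exclusion criterion 3 in Section 5.4.2 admits candidates with organ-confined prostate cancer once hormonal therapy has begun, while Section 5.6.6.1 makes no matching exception.

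**The case against.** The Appendix 1 tables are organised by mechanism, so a CYP3A4 comment can be read as answering only the CYP3A4 question. The P-gp list supports this: verapamil and diltiazem are allowed as CYP3A4 inhibitors, yet P-gp inhibitors are to be avoided if possible. The QT rule has an exception for essential use. No one would plausibly take an interaction table as permission to give nilotinib or vemurafenib in this trial. This is a reasonable reading, but the protocol does not state it, and Section 5.6.6.1 itself names fluconazole as usable directly after the QT prohibition.

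On strong inhibitors generally, one text says avoid and the other says prohibited unless necessary. A reader might infer opposite instructions. The documents do not support that: both permit use when needed and both call for a dose change. What remains is a smaller wording mismatch.

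On 20 mg/day, the synopsis opens its dose-reduction list by mentioning discontinuation as well as the two steps, which might be taken to cover the case. However, its strong-inhibitor item gives only the two steps, and the opening sentence of Section 5.6.4.4 does not mention discontinuation. The gap therefore remains.

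A reader might also fault the 30-to-20 mg step for not fully offsetting a 2-fold rise. Section 5.2.4 gives the figure and the step together, and nothing says that the step must offset it. That is a dosing choice, not a contradiction.

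Finally, withdrawal under Section 5.4.5 for using a prohibited drug is discretionary and applies only without prior approval by the investigator and sponsor, so it does not follow automatically from these mismatches.

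**Conclusion.** Two conflicts stand in the current text: the 20 mg/day case, and the unstated precedence for three QT-listed drugs and seven antineoplastics. The strong-inhibitor wording is a lesser mismatch.

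The approximate doubling applies only to a subject already at 20 mg/day without an inhibitor who then starts a strong one. It rests on ketoconazole data in volunteers, on proportionality extended to 20 mg, and on parent drug alone. Section 5.2.4 gives no figure for the active metabolite AC886, which is also metabolised by CYP3A4. The ratio describes exposure and does not by itself quantify QT risk.

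Two stronger conclusions are tempting. One is that nothing is done at 20 mg/day and QT risk is uncontrolled. That is not so: scheduled ECGs, interruption, discontinuation and drug review all apply, although the QTcF-triggered actions follow observed prolongation. The other is that an allowed kinase inhibitor would confound the antileukaemic endpoints. The documents give neither an expected frequency of use nor an effect size, so that is speculation.

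Sample size, type I error and power are unaffected. The point should be fixed because these are conflicting safety instructions and the repair is cheap.

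**What to change.** Reconcile the synopsis dose-reduction text, Sections 5.2.4, 5.6.4.4 and 5.6.6.1, and Appendix 1 so that:
- each listed drug has one status;
- the protocol states whether the QT and antineoplastic prohibitions take precedence over the CYP3A4 comments, including how the prostate-cancer eligibility exception fits with the antineoplastic rule;
- strong inhibitors are described in the same words in Section 5.6.6.1 and Appendix 1;
- the passages governing a subject at 20 mg/day who needs a strong inhibitor agree with one another.

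The sponsor's clinical pharmacology and medical staff must decide which rule stands; no dose or rule is proposed here. The cost is a wording amendment to these sections and the appendix tables, plus a memo to sites. No new procedure or data collection is needed.

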5.6.6.2. Supportive Care Guidelines

Subjects will receive appropriate best supportive care throughout the study.

5.6.7. Treatment Compliance

Trained medical personnel will administer MEC, and FLAG-IDA in the study site setting. Treatment with quizartinib and LoDAC will be initiated in the clinic. Compliance must be monitored by reviewing the subject's returned study treatment supply at every visit and by completing the drug accountability record.

5.7. Study Variables

5.7.1. Primary Efficacy Variable

The primary efficacy variable is overall survival, defined as the time from randomization until death from any cause. Complete definitions of efficacy variables are given in Section 7.2.

5.7.2. Secondary Efficacy Variable

The secondary variable is EFS, defined as the time from randomization until documented refractory disease, relapse after CRc, or death from any cause, whichever is observed first. Complete definitions of efficacy variables are given in Section 7.2.

5.7.3. Additional Efficacy Variables

Additional efficacy variables will be evaluated as follows:

- Leukemia-free survival is the time from the first documented response (CR, CRp, or CRi) until documented relapse or death from any cause.
- Composite complete remission (CRc) rate is the percentage of subjects achieving a best response of CR, CRp, or CRi.
- Complete remission (CR) rate is the percentage of subjects achieving a best response of CR.
- Duration of composite complete remission (CRc) is the time from the first documented CRc (CR+CRi+CRp) until documented relapse.
- Duration of complete remission (CR) is the time from the first documented CR until documented relapse.

5.7.4. Transplantation rate (bridge to transplant) is the percentage of subjects undergoing HSCT directly following protocol specified treatment with no intervening AML therapy. Safety Variables

Safety will be assessed with physical examinations, vital sign determinations, AE evaluations, 12-lead ECGs, ECOG performance scores, and clinical laboratory tests (hematology, serum chemistry, and urinalysis results).

All AEs reported from Day 1 to the 30-Day Follow-up visit, or to the day of withdrawal of the subject from the study, will be evaluated for clinical significance by the Investigator. An AE will be considered clinically significant if it results in inability to perform usual activities, requires acute medical intervention, or in any other way suggests a significant hazard to the subject. AEs will be graded according to Version 4.03 of the National Cancer Institute Common Terminology Criteria for Adverse Events (CTCAE v4.03) (<http://ctep.info.nih.gov>).

5.7.5. Pharmacokinetic and Exposure-response Variables

Pharmacokinetics and Concentration-QTcF Relationship of quizartinib and AC886 will be evaluated. Other exposure-response relationships with efficacy or safety variables may be explored.

5.7.6. Additional Variables

The following will be evaluated:

- FLT3-ITD status and allelic ratio
- Mutations in the kinase and juxtamembrane domains of FLT3-ITD and other mutations known to be associated with AML, determined with bone marrow or whole blood samples
- Pharmacogenomics
- Pharmacoproteomic evaluations

5.7.7. Pharmacoeconomic Variables

Resource utilization will be assessed by evaluating the following parameters:

- Concomitant medications and procedures
- Hospitalizations
- Unscheduled clinic visits
- Emergency room visits
- Skilled nursing facility care
- Hospice care

5.8. Study Schedule

The schedule of study activities and assessments for subjects receiving quizartinib is presented in [Table 3](#); the schedule of study activities and assessments for subjects receiving quizartinib after HSCT is presented in [Table 4](#); the schedule of study activities and assessments for subjects receiving salvage chemotherapy is presented [Table 5](#); and the schedule of study activities and assessments after treatment is presented in [Table 6](#).

Table 3 Schedule of Activities and Assessments for Subjects Receiving Quizartinib

Activity	Screening (≤14 days from randomi- zation)	Cycle 1				Cycle 2		Cycle 3	Cycle 4 and Subsequent cycles
		D 1	D 2 and D 8 ±1	D 15 ±1	D 16 ±1	D 1 ±3	D 15 ±3	D 1 ±3	D 1 ±3
Written informed consent	X								
Medical and disease history and demographics	X								
Physical examination	X	X	X	X		X	X	X	X
Vital sign determinations	X	X	X	X		X	X	X	X
ECOG performance status evaluation	X	X				X		X	X
Assessment of prior and concomitant medications	X ^a	X	X	X		X	X	X	X
Pregnancy test for women of childbearing potential	X ^b	X ^b							X ^b
Determination of coagulation profile (PT/INTR)	X								
Chest X-rays (posterior/anterior and lateral)	X								
12-lead ECG (triplicate)	X ^c	X ^c	X ^c	X ^c		X ^c		X ^c	X ^c
Clinical laboratory tests (hematology; chemistry; urinalysis)	X	X ^d	X ^d	X ^d		X ^d	X	X ^d	X
MUGA scan or ECHO ^e	X								
Bone marrow aspiration or biopsy	X ^f					X ^f		X ^f	X ^f
Collection of bone marrow and whole blood specimen for central laboratory FLT3 mutation determination and other AML-associated mutations ^g	X								
AE/SAE assessment		X	X	X		X	X	X	X
Collection of plasma samples for PK determinations		X ^h	X ^h	X ^h	X ^h	X ^h		X ^h	
Collection of samples for pharmacogenomics and proteomic determinations ⁱ		X							
Administration of quizartinib at the study site ^j		X	X	X	X	X		X	
Review of returned study medication and assessment of compliance (Day 8 and subsequently)			X	X		X	X	X	X

See footnotes on the next page

^a Including medications received within 28 days prior to screening.

- ^b Women of childbearing potential must have a negative serum test result (minimum sensitivity 25 IU/L or equivalent units of hCG) at screening and a urine test on Day 1 of Cycle 1 before dosing, and every 3 months during the treatment phase.
- ^c Triplicate ECGs to be obtained at screening; on Day 1 of Cycle 1 before dosing and 2, 4 and 6 hours after dosing; on Day 2 and 8 of Cycle 1 before dosing and 2 to 4 hours after dosing; on Day 15 of Cycle 1 before dosing and 2, 4 and 6 hours after dosing; on Day 1 of Cycles 2 and 3 before dosing and 2 to 4 hours after dosing; and on Day 1 of all subsequent cycles with no time restriction. Following dose escalation, triplicate ECG determinations should be performed at least once weekly for 2 weeks to monitor QTcF prolongation.
- ^d Obtained before dosing. Clinical laboratory evaluations are detailed in Section 8.6, [Table 8](#).
- ^e MUGA scans or ECHO are to be performed at screening on all subjects unless a MUGA scan performed within 1 month of screening revealed LVEF \geq 45%.
- ^f Bone marrow aspiration and biopsy for morphology determination are preferred, but biopsy may be omitted if the aspirate is considered to be adequate. Bone marrow samples are required at screening for central testing (within 14 days prior to randomization; bone marrow examinations outside this window may be acceptable if agreed by the Medical Monitor), on Day 1 of Cycle 2 and Cycle 3, at the early termination/end of treatment visit, and as clinically indicated. Bone marrow assessments will be repeated on Day 1 of each subsequent cycle unless the subject has already achieved CR, CRp, or CRi. In that event, bone marrow testing will be repeated after every 3 subsequent cycles, unless there is evidence of relapse. A central laboratory will review a screening specimen to confirm the diagnosis.
- ^g The following specimens must be collected and sent to Genoptix for central analysis. A bone marrow and peripheral blood sample should be obtained at screening (at approximately the same time) for determination of FLT3-ITD status. A bone marrow sample should be obtained at treatment discontinuation or relapse. The sample may also be tested for FLT3 point mutations and mutations in other AML-associated genes.
- ^h Blood samples for PK determinations will be collected on Day 1 and Day 15 of Cycle 1 before dosing and 1, 2, 4, 6, and 24 hours after dosing. The 24-hour samples must be collected before quizartinib dosing on Day 2 and Day 16. Samples will also be collected on Day 8 of Cycle 1 before dosing and 2 to 4 hours (taken immediately after ECG) after dosing. Thereafter, samples will be collected before dosing and 2 to 4 hours (taken immediately after ECG) after dosing on Day 1 of Cycles 2 and 3. At each time point, 2 mL of blood will be collected. When an ECG is performed at the same study time point, the PK specimen should be taken immediately afterwards.
- ⁱ If consent is provided, blood sample (Pax gene DNA, Pax gene RNA, and PBMC) and buccal swab on Day 1 of Cycle 1 before dosing.
- ^j Quizartinib must be taken at the clinic on Cycle 1: Days 1, 2, 8, 15, and 16; Cycle 2: Day 1; and Cycle 3: Day 1. On other days the subject may take quizartinib at home. Quizartinib should be taken in the morning. Please refer to the dosing guidelines in [Section 5.6.4.3](#) regarding required dose escalation at Day 16 if the subject meets the criteria for dose escalation. A second opportunity for dose escalation is available after the first 28-day cycle if the subject has not achieved a CRc. In addition, subjects who achieved a response (CR, CRi, CRp, or PR) at any time and who subsequently relapsed will be assessed for dose escalation provided they meet the same criteria defined in [Section 5.6.4.3](#).

Table 4 Schedule of Activities and Assessments for Subjects Receiving Quizartinib After HSCT

Activity	Cycle 1 (Post-HSCT)			Cycle 2 and subsequent cycles (Post-HSCT)
	D 1	D 8 ±1	D 15 ±1	D 1 ±3
Physical examination	X ^a	X	X	X
Vital sign determinations	X ^a	X	X	X
ECOG performance status determination	X ^a			X
Assessment of concomitant medications	X ^a	X	X	X
12-lead ECG (triplicate)	X ^b	X ^b	X ^b	X ^b
Pregnancy test for women of childbearing potential	X ^c			X ^c
Clinical laboratory tests (hematology; chemistry; urinalysis)	X ^a	X	X	X
Bone marrow aspiration or biopsy	X ^d			X ^d
Specimen collection for central laboratory assessment of FLT3 mutations using bone marrow	X ^e			
AE/SAE assessment	X	X	X	X
Administration of quizartinib at the study site	X ^f	X ^f	X ^f	
Review of returned study medication and assessment of compliance		X	X	X

^a Performed before dosing and results reviewed before dosing. Blood draws may be taken previous day.

^b Triplicate ECGs to be obtained on Day 1 of Cycle 1 post-HSCT before dosing, 2, and 4 hours after dosing; on Day 8 of Cycle 1 post-HSCT; Day 15 of Cycle 1 before dosing (including a determination of whether dose escalation is appropriate); Day 1 of Cycle 2 post-HSCT and all subsequent cycles. Following dose escalation, triplicate ECG determinations should be performed at least once weekly for 2 weeks to monitor QTcF prolongation.

^c Women of childbearing potential must have a negative urine pregnancy test before the start of study treatment and every 3 months during the treatment phase.

^d Bone marrow aspiration and biopsy for morphology determination are preferred, but biopsy may be omitted if the aspirate is considered to be adequate. Bone marrow samples are required on Day 1 of Cycle 1 post-HSCT (may be taken within 14 days prior to the first dose of study drug; this window may be extended after consultation with the Medical Monitor), on Day 1 of Cycle 4 and every 3 cycles subsequently, at the early termination/end of study visit, and as clinically indicated.

^e A bone marrow sample should be obtained at Day 1 Cycle 1 (may be taken with 14 days prior to dosing) for central determination of FLT3 mutations and mutations in other genes. FLT3 test result is not required to start quizartinib following transplantation.

^f Quizartinib should be taken in the morning.

Table 5 Schedule of Activities and Assessments for Subjects Receiving Salvage Chemotherapy

Activity	Screening (≤14 days from random- ization)	Cycle 1				Cycle 2	
		D 1	D 2 and D 8 ±1	D 15 ±3	D 29 ±14	D 1 ±3	D 15 ±3
Written informed consent	X						
Medical and disease history and demographics	X						
Physical examination	X	X	X	X		X	X
Vital sign determinations	X	X	X	X		X	X
ECOG performance status determination	X	X		X		X	X
Assessment of prior and concomitant medications	X ^a	X	X	X		X	X
Pregnancy test for women of childbearing potential	X ^b	X ^b					
Determination of coagulation profile (PT/INR)	X						
Chest X-rays (posterior/anterior and lateral)	X						
12-lead ECG (triplicate)	X ^c	X ^c	X ^c	X ^c		X ^c	X ^c
Clinical laboratory tests (hematology; chemistry; urinalysis)	X ^d	X ^d	X ^d	X ^d		X ^d	X ^d
MUGA scan or ECHO	X ^e					X ^e	
Bone marrow aspiration or biopsy	X ^f				X ^f		
Collection of bone marrow and whole blood specimen for central laboratory FLT3 mutation determination and other AML-associated mutations	X ^g						
AE/SAE assessment		X	X	X		X	X
Collection of samples for pharmacogenomic and proteomic determinations		X ^h					
Administration of MEC or FLAG-IDA at the study site					X ⁱ		
Administration of low dose cytarabine (LoDAC)					X ^j		

See footnotes on the next page

- ^a Includes medications received within 28 days prior to screening.
- ^b Women of childbearing potential must have a negative serum test result (minimum sensitivity 25 IU/L or equivalent units of hCG) at screening and a urine test on Day 1 of Cycle 1 before dosing and every 3 months during the treatment phase.
- ^c Obtained before dosing. Subjects receiving MEC or LoDAC will undergo ECGs on Day 1 of each cycle; FLAG-IDA will undergo ECGs on Day 2 of each cycle instead of Day 1. All salvage chemotherapy subjects will have ECG on Days 8 and 15 Cycle 1 and Day 15 Cycle 2.
- ^d Obtained before dosing. Clinical laboratory evaluations are detailed in Section 8.6, [Table 8](#).
- ^e MUGA scans or ECHO are to be performed at screening unless a MUGA scan performed within 1 month of screening revealed LVEF \geq 45%. Subjects receiving FLAG-IDA should have a MUGA scan or ECHO before dosing on Day 1 of Cycle 2, to determine their eligibility for a second cycle.
- ^f Bone marrow aspiration and biopsy for morphology determination are preferred, but biopsy may be omitted if the aspirate is considered to be adequate. Bone marrow samples are required at screening (within 14 days prior to randomization; bone marrow examinations outside this window may be acceptable if agreed by the Medical Monitor). For high intensity chemotherapy (MEC or FLAG-IDA), bone marrow samples are also required on Day 29 (\pm 14 days) of each cycle of therapy, and at the early termination/end of treatment visit, and as clinically indicated. For LoDAC, bone marrow samples are also required on Day 1 of Cycle 2 and Day 1 of Cycle 3. If a subject continues to receive LoDAC past Cycle 2, bone marrow assessments will be repeated on Day 1 of each subsequent cycle unless the subject has already achieved a CR, CRp, or CRi. In that event, bone marrow testing will be repeated after every 3 subsequent cycles, unless there is evidence of relapse. Additionally for LoDAC, bone marrow samples are required at the early termination/end of treatment visit, and as clinically indicated.
- ^g A bone marrow and peripheral blood sample should be obtained at screening (at approximately the same time) for determination of FLT3-ITD status. A bone marrow sample should be obtained at treatment discontinuation or relapse. The sample may also be tested for FLT3 point mutations and mutations in other AML-associated genes.
- ^h If consent is provided, blood sample (Pax gene DNA, Pax gene RNA, and PBMC) and buccal swab on Day 1 of Cycle 1 before dosing.
- ⁱ Additional study site visits are required for subjects receiving MEC (Days 1 through 5) or FLAG-IDA (Days 1 through 6). MEC and FLAG-IDA are administered for up to 2 cycles, depending on response and safety assessments.
- ^j Treatment with LoDAC may continue past Cycle 2 and subsequent cycles will follow same procedures as Cycle 2. . Low dose cytarabine should be administered for 10 days in a 28 day cycle in the clinic unless arrangements can be made for administration outside of the clinic. If dosed outside the clinic, a review of medication returned and assessment of compliance must be conducted at the beginning of each cycle.

Table 6 Schedule of Activities and Assessments After Treatment

Activity	End of Treatment Visit ^a	Cross-Over ^f	30-Day Follow-Up	Long-term Follow-Up	Early Termination / End of Study ^h
Written informed consent		X			
Physical examination	X ^b	X			
Vital sign determinations	X ^b	X			
ECOG performance status determination	X ^b	X			
Assessment of concomitant medications	X	X	X		X
Serum pregnancy test for women of childbearing potential	X				
Determination of coagulation profile (PT/INR)		X			
12-lead ECG (triplicate)	X	X			
Clinical laboratory tests (hematology; chemistry; urinalysis)	X ^b	X ^g			
Bone marrow aspiration or biopsy	X ^c				
Assessment of FLT3 mutations using bone marrow	X ^d				
Collection of blood for pharmacogenomic and proteomic determinations	X ^e				
AE/SAE assessment	X	X	X ^h		X
Review of returned study medication and assessment of compliance, for subjects receiving quizartinib or LoDAC	X				X ⁱ
Determination of remission status, subsequent antileukemic treatments and their outcomes, and survival		X	X ^h	X ⁱ	
Reason for withdrawal					X

^a The end of treatment visit should occur within 7 days of the last dose of quizartinib. If quizartinib is discontinued a form must be completed so subject can proceed to HSCT. Additionally subjects moving onto HSCT must have the 30 Day Follow-up phone contact and will be evaluated in Long-Term Follow-up schedule until they resume quizartinib dosing. For subjects receiving chemotherapy the EOT visit corresponds to Day 29 of the last cycle. Assessment of best response to chemotherapy should be conducted at Day 29 (±14 days) or prior to starting subsequent AML therapy.

^b These assessments need not be repeated if they were performed at a regularly scheduled visit within 3 days of the end of treatment visit.

^c Bone marrow aspiration and biopsy to determine response status are preferred, but biopsy may be omitted if the aspirate is considered to be adequate. For subjects receiving chemotherapy the bone marrow and response assessment should be conducted at Day 29 ± 14 days.

^d FLT3 mutation analysis will be performed for subjects in the quizartinib arm only. A bone marrow sample (or peripheral blood sample if marrow cannot be obtained) should be obtained at the end of treatment for determination of FLT3-ITD status. The sample may also be tested for FLT3 point mutations and mutations in other AML-associated genes.

- ^e If consent is provided, collection of blood (Pax gene RNA) at end of treatment visit
- ^f Screening procedures can be completed within 3 days of the end of treatment visit to determine that subjects meet inclusion criteria and do not meet exclusion criteria. There is no washout period required between stopping salvage chemotherapy and starting treatment with quizartinib.
- ^g For the Cross-over period, only hematology and chemistry samples will be collected. Clinical laboratory tests need not be repeated if they were performed within 3 days at the End of Treatment visit, and 3 days prior to the start of quizartinib treatment.
- ^h Telephone contact with the subject is sufficient unless any assessment must be repeated for resolution of treatment-related AEs.
- ⁱ Early Termination/End of Study is for subjects withdrawing consent, discontinuing treatment and/or follow up. Review of returned medication is required for subjects receiving study drug at time of withdrawal.
- ^j Telephone contact every 3 months.

